I.d. Summary of background and current gaps in knowledge. DKD is highly prevalent, particularly among older adults, and leads to substantial morbidity and mortality due to progressive kidney and cardiovascular disease. While tight glycemic control and RAAS inhibitors help prevent the incidence and progression of DKD, rates of adverse renal and cardiovascular consequences remain unacceptably high. Cholecalciferol and ω -3 FA are promising interventions for the prevention and treatment of DKD, because

animal-experimental data suggest they have substantial reno-protective effects, early human data suggest these effects have clinical relevance, and each intervention is relatively accessible, inexpensive, and safe. Thus, it is possible that cholecalciferol and/or ω -3 FA are appropriate for wide-spread use to prevent and treat DKD in the large and growing population of older persons with diabetes. This hypothesis requires rigorous testing in well-controlled clinical trials.

II. SPECIFIC AIMS

Diabetic kidney disease (DKD) is a common and morbid complication of diabetes mellitus. Preventing the development and progression of DKD is a critical goal for improving long-term health outcomes of the growing diabetes population and for reducing the overall burden of kidney disease in the United States. Therefore, there is an urgent need for additional, complementary interventions to prevent and treat DKD. This need is greatest among older adults because diabetes and kidney disease are highly prevalent among older adults and kidney disease is among the strongest risk factors for mortality in this group. Vitamin D and omega-3 fatty acids (ω -3 FA) are two of the most promising interventions for DKD prevention and treatment. Because cholecalciferol and ω -3 FA are relatively safe, inexpensive, and widely available, they may offer opportunity to substantially reduce the burden of DKD in large populations. Prior to widespread implementation, however, these hypothesized benefits should be rigorously tested in well-powered clinical trials. Therefore, among older adults with diabetes, we aim:

SPECIFIC AIM 1: To test whether cholecalciferol (vitamin D₃, 2000 IU per day) prevents the development and progression of DKD, compared with placebo.

Hypothesis 1a: Cholecalciferol slows progression of albuminuria over 4 years of therapy.

Hypothesis 1b: Cholecalciferol reduces loss of GFR over 4 years of therapy.

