V.d. Blood Collection. Each participant will be sent a standardized blood collection kit after 4 years of study participation. This kit will be identical to the blood collection kit used by the parent VITAL trial for collection of baseline (pre-randomization) blood samples. (Baseline blood samples will be collected only by the parent VITAL trial under the parent VITAL trial IRB approval and with separate informed consent. These samples will be made available for use in the VITAL Diabetes ancillary study.) The kit will include supplies and instructions for having blood drawn into two EDTA tubes, one heparin tube, and one citrate tube; a gel-filled freezer pack; and an overnight courier air bill. We anticipate that most participants will have their blood drawn by their own healthcare providers or in another healthcare or blood-drawing facility. Participants will be instructed to record the time of venipuncture and the time of their last meal. They will be instructed to immediately send their sample to the VITAL laboratory at the BWH Division of Preventive Medicine in the freezer packs. Upon receipt, samples will be processed using the same protocols as the parent VITAL trial, in order to avoid laboratory errors. Blood samples will be centrifuged to separate plasma and red blood cells, each aliquoted into 2-ml Nunc vials. EDTA-plasma samples will be thawed for measurements of creatinine, cystatin C, C-reactive protein, 25-hydroxyvitamin D, and eicosapentaenoic acid and docosahexaenoic acid. Red blood cells will be thawed for measurement of hemoglobin A1c.

V.e. Interventions. All interventions will be provided by the parent VITAL trial and are included in the IRB application for the parent VITAL trial. For completeness, these are described below.

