V.e.1. Cholecalciferol intervention. Active cholecalciferol (vitamin D₃) and matching inert placebo will be provided by Pharmavite LLC. Cholecalciferol is recommended by many experts as the optimal form of vitamin D supplementation based on its known dose-response effects on 25(OH)D concentration, documented long-term safety, and proven benefits in fracture reduction when used with calcium in the setting of osteoporosis.^{61, 62, 138} Each active cholecalciferol study pill will contain 2000 IU (40 µg) cholecalciferol. This dose was chosen to maximize the separation in 25-hydroxyvitamin D concentration attained between treatment groups while maintaining safety. Specifically, cholecalciferol 2000 IU daily is conservatively anticipated to raise mean 25-hydroxyvitamin D concentration by approximately 16 ng/mL, while maintaining total daily cholecalciferol intake at or below the no-observed-adverse-effect level (NOAEL) specified by the Institute of Medicine, and well below the 4000 IU NOAEL specified by the European Commission Scientific Committee on Food, with allowance for nonstudy use up to 800 IU/d.^{62, 138-140} Study medications will be dispensed in calendar packs, with participants asked to take one pill (cholecalciferol or placebo) each day. Participants will be instructed to discontinue their study pills if, during follow-up, they receive a diagnosis of kidney stones or hypercalcemia.

V.e.2. Omega-3 fatty acid intervention. Active fish oil (1000 mg capsule containing 840 mg EPA + DHA) and matching inert placebo will be provided by Pronova BioPharma ASA of Norway. Each active soft-gel capsule will contain a total EPA+DHA dose of 840 mg/d, the highest dose of EPA + DHA currently available in a 1000 mg capsule. We believe that this dose provides the best balance of feasibility, efficacy and safety. We seek to

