VII.a. Potential adverse effects of study interventions. The main risks of this study arise from the interventions of the parent VITAL trial, not the VITAL Diabetes ancillary study described herein. The parent VITAL trial will test a dose of 2000 IU (40 µg) per day of vitamin D₃ (cholecalciferol) and 840 mg/d of EPA+DHA in VITAL. We believe that these doses provide the best balance of efficacy and safety, based on careful review of the literature and extensive consultation with numerous nutritional experts. We seek to obtain an adequate difference in vitamin D and EPA+DHA levels between the treatment and placebo groups to detect health benefits, and there appear to be few safety issues associated with these doses. For vitamin D, the selected dose is lower than the tolerable upper intake level (UL) for vitamin D₃ (50 µg, or 2000 IU) set by the Food and Nutrition Board of the Institute of Medicine (IOM) and the European Commission Scientific Committee on Food (EC SCF). Also, because we will exclude from the trial persons who report supplemental vitamin D intakes >800 IU/d, the selected dose ensures that no participants will be taking a supplemental vitamin D dose above 2800 IU, which is well below the 4000 IU NOAEL specified by the EC SCF. To further ensure participants' safety, we will exclude from the trial persons with a history of kidney stones, hypercalcemia, renal failure, cirrhosis, or sarcoidosis or other granulomatous disease, and will obtain calcium and PTH levels in a random subsample of participants. For fish oil, there are no specific exclusions necessary except for those currently taking the supplement and unwilling to forego use during the trial.

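### Does the claim that the vitamin D dose lies below the upper intake level fail because 2000 IU is written as both 40 µg and 50 µg?

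*Combined protocol and SAP*

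**What the plan says.** Section V.e.1 describes the pill: "Each active cholecalciferol study pill will contain 2000 IU (40 µg) cholecalciferol". Section VII.a repeats the pair at the start of the risk discussion: "The parent VITAL trial will test a dose of 2000 IU (40 µg) per day of vitamin D₃ (cholecalciferol"). Three sentences later it offers a safety comparison: "the selected dose is lower than the tolerable upper intake level (UL) for vitamin D₃ (50 µg, or 2000 IU"), citing the Institute of Medicine and a European Commission committee for that limit.

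Elsewhere the dose is given in IU alone, for example in Specific Aim 1: "To test whether cholecalciferol (vitamin D₃, 2000 IU per day) prevents the development and progression of DKD, compared with placebo". The other vitamin D quantities are also in IU: the 800 IU/d non-study allowance (Table 1, V.e.1, VII.a), the 2800 IU ceiling (VII.a) and the 4000 IU no-observed-adverse-effect level, or NOAEL (V.e.1, VII.a).

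Section V.e makes clear that this ancillary protocol does not set the dose: "All interventions will be provided by the parent VITAL trial and are included in the IRB application for the parent VITAL trial". It describes the interventions only for completeness.

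**The concern.** One quantity, 2000 IU of vitamin D₃, is equated with 40 µg when it is the dose and with 50 µg when it is the limit. A reader working in IU, the protocol's usual unit, finds a dose equal to the limit under a sentence saying that it is lower. Only the µg figures show a gap.

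The sentence is the first numerical support for the vitamin D dose in the section where an ethics committee would look for the safety case. If the gap comes only from a unit slip, the section claims a margin that its own numbers do not show. The 2016 addendum revises only the analytic plan, so this text is current.

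**Working it through.** **Inputs**
- Dose: 2000 IU, 40 µg (V.e.1 and VII.a).
- Upper intake level (UL): 2000 IU, 50 µg (VII.a).
- Permitted non-study vitamin D: 800 IU/d (Table 1, V.e.1, VII.a).
- Ceiling on supplemental intake: 2800 IU (VII.a).
- European NOAEL: 4000 IU (V.e.1, VII.a).

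**The plan's own comparison**
- In µg: 40/50 = 0.80, so the dose is lower, as stated.
- In IU: 2000/2000 = 1.00, so the dose equals the limit.

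**Implied conversions** (IU divided by µg)
- Dose pair: 2000/40 = 50 IU per µg.
- UL pair: 2000/50 = 40 IU per µg.

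The pairs conflict, so at least one figure is wrong.

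**What each possible slip would mean**

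| Figure in error | Conversion that then applies | Corrected figure | Dose / UL | Is the dose lower? |
|---|---|---|---|---|
| Dose in µg | 40 IU per µg | 2000/40 = 50 µg | 50/50 = 1.00 | No, equal |
| UL in µg | 50 IU per µg | 2000/50 = 40 µg | 40/40 = 1.00 | No, equal |
| UL in IU | 50 IU per µg | 50 × 50 = 2500 IU | 2000/2500 = 0.80 | Yes |

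The dose in IU is not a comparable candidate. It is stated in the opening summary, the Specific Aims, V.e.1 and VII.a, and it underlies the ceiling (2000 + 800 = 2800 IU), so it is not a slip in one place. The three cases in the table cannot be told apart from the documents.

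**What depends on the sentence**
- *The other numerical safety argument.* Section VII.a says that "the selected dose ensures that no participants will be taking a supplemental vitamin D dose above 2800 IU" and sets that total against the 4000 IU NOAEL: 2800/4000 = 0.70. No µg figure enters.
- *The Institute of Medicine benchmark in V.e.1.* The claim there is of "maintaining total daily cholecalciferol intake at or below the no-observed-adverse-effect level (NOAEL) specified by the Institute of Medicine". No figure is printed for that level, so the claim neither uses nor contradicts the µg values.
- *Safeguards.* The exclusions for kidney stones, hypercalcemia, renal failure, cirrhosis and granulomatous disease, the calcium and PTH subsample, the instruction on study pills after a diagnosis of stones or hypercalcemia, the side-effect questionnaires and the monitoring board's comparisons are all stated without reference to the UL.
- *Statistics.* Neither power section (VI.h, and D16 of the addendum) takes the dose or the UL as an input. The models use assigned treatment as a yes/no term.

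**The case for a change.** The case for acting is that a safety statement should be reproducible from its own numbers, and this one is not. An extraction fault is unlikely, because 40 µg appears in two separate sections and the wording agrees with 40 against 50. In two of the three plausible cases the dose equals the limit and the sentence is false. In the third, a printed limit is wrong. Correcting the text would cost almost nothing. One of the candidate errors also lies in the description of the pill, where 40 against 50 µg is a ratio of 50/40 = 1.25.

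The conflict stands: the figures are inconsistent, and the comparison is unsupported as printed. It is too strong, however, to say that the claim holds only because of the mismatch, since under the third case it is true with a single conversion.

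The pill point does not carry further. The two descriptions of the pill agree with each other, IU is the unit used for the dose throughout, and this document does not govern manufacture. Nothing here shows that any participant would receive something other than what the parent trial specifies.

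**Conclusion.** The inconsistency is real but clerical. The same 2000 IU is printed as 40 µg and as 50 µg, which gives a dose-to-limit ratio of 0.80 or 1.00 according to unit. The IU and µg figures in V.e.1 and VII.a must be reconciled as a matter of text. I take no view on which figure, dose or limit is right, and the documents do not settle it.

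No change to the plan follows. Reconciliation would alter a sentence in a descriptive risk paragraph and perhaps a parenthesis in V.e.1. It would alter no eligibility criterion, monitoring rule, endpoint, power figure or analysis. The comparison with the 4000 IU NOAEL, at 0.70, is unaffected by the µg conflict.

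This rests on two assumptions: that the parent trial's own specification fixes the content of the pill, as V.e indicates, and that the 2000 IU repeated throughout is the intended dose statement.

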Submitted in NIH grant renewal application 3/2/2015
Implemented upon funding 2/24/2016

15. Data analysis

15a. Descriptive analyses. We will describe creation of the VITAL diabetes sub-cohort according to CONSORT guidelines, including numbers of participants who consent to VITAL participation; report a diagnosis of diabetes; are approached for the DKD ancillary study; enroll in the DKD ancillary study; and complete year 2 and 5 year biosample collections. We will document reasons that participants do not complete the proposed studies. Among participants recruited into the DKD ancillary study, we will compare baseline characteristics of those who do and do not return at least one follow-up biosample collection. Among participants who return a follow-up biospecimen, we will describe by treatment assignment baseline characteristics and changes in clinical characteristics over the course of the study.

15b. Study outcomes. With an extension of follow-up from 2 to 5 years, we will have sufficient time to effectively evaluate change in estimated GFR (eGFR), a clinically relevant outcome.¹⁷⁵⁻¹⁷⁹ Therefore, if this competitive renewal is funded, change in eGFR from baseline to year 5 will supplant 2-year changes in albuminuria and eGFR as our primary study outcome. Change in eGFR will be calculated and summarized by treatment group as $[eGFR_5 - eGFR_0]$, where $eGFR_5$ represents eGFR at follow-up (year 5) and $eGFR_0$ represents eGFR at baseline. As secondary outcomes, we will examine changes in urine ACR from baseline to years 2 and 5, time to the development of rapid eGFR loss (loss of eGFR $\geq 40\%$ from baseline to year 2 or 5),¹⁷⁵⁻¹⁷⁹ and time to a composite of rapid eGFR loss, end stage renal disease (maintenance dialysis or kidney transplant verified by medical records review), or death. The composite outcome addresses large changes in eGFR which have particularly high clinical importance and reduces the potential impact of competing risks that preclude assessment of eGFR at follow-up.

15c. Intention to treat and missing data. Analyses will be performed in accordance with the intent-to-treat principle, meaning that all participants who return at least one follow-up biosample will be included in analyses, regardless of adherence or other characteristics observed after randomization. Multiple imputation for study participants missing year 5 eGFR will be conducted using chained equations, utilizing baseline data as well as eGFR and urine ACR data available at year 2.¹⁸⁰ Results from 10 imputation datasets will be combined using Rubin's rules.¹⁸¹

15d. Treatment interaction. We will assess for interaction of the study interventions (vitamin D and omega-3 fatty acids) for the primary outcome.¹⁸² We will use a linear mixed model to test for interaction:¹⁸³

$$\text{Equation 1: } eGFR_{ij} = \beta_0 + \beta_1(\text{vitamin D}_i) + \beta_2(\omega-3 \text{ FA}_i) + \beta_3(\text{vitamin D}_i \times \omega-3 \text{ FA}_i) + \beta_4(\text{vitamin D}_i \times t_{ij}) + \beta_5(\omega-3 \text{ FA}_i \times t_{ij}) + \beta_6(\text{vitamin D}_i \times \omega-3 \text{ FA}_i \times t_{ij}) + a_i + e_{ij}$$

where i denotes the i th participant and $j=0,2,5$ represents the time period, t is time modeled categorically, (vitamin D) is active vitamin D treatment assignment (yes/no), (ω -3 FA) is active omega-3 treatment assignment (yes/no), a_i is a random effect for patient, and e is statistical error. A p value < 0.05 for β_6 will be interpreted as evidence of interaction. If we observe interaction, all analyses will separately compare each of the 3 active treatment groups to the treatment group which receives (placebo + placebo). If there is no evidence of interaction, as hypothesized, all participants assigned to any active vitamin D will be compared to all participants assigned to placebo vitamin D, and all participants assigned to any active omega-3 fatty acids will be compared to all participants assigned to placebo omega-3 fatty acids.

15e. Hypothesis testing. The primary outcome is a continuous variable which will be tested using a linear mixed model with random intercepts. To test whether the change in eGFR differs by vitamin D treatment assignment in the absence of interaction with omega-3 fatty acids, we will test:

$$\text{Equation 2: } eGFR_{ij} = \beta_0 + \beta_1(\text{vitamin D}_i) + \beta_2(t_{ij}) + \beta_3(\text{vitamin D}_i \times t_{ij}) + a_i + e_{ij}$$

where β_3 represents the difference in change in eGFR over time, comparing those on active vitamin D₃ to those on placebo. The corresponding 95% confidence interval and p-value reflect statistical significance of the treatment effect. We will use this model to describe treatment effects at years 2 and 5 but reserve statistical inference for year 5 alone. Corresponding equations will test the effect of omega-3 treatment assignment on eGFR as well as treatment effects on urine ACR, analyzed as a log-transformed continuous variable. The relatively large sample size makes it likely that few or no substantial differences in baseline characteristics will be present. In the event that any baseline characteristics are not balanced between treatment groups, sensitivity analyses will add to the model additional terms for such baseline characteristics. If we observe differences by treatment group in medication use (e.g. glucose-lowering or antihypertensive medications) or

laboratory covariates (e.g. hemoglobin A1c, CRP, IL-6) over follow-up, we will explore whether such differences may mediate or attenuate treatment effects by adding terms for these covariates to the model. We will assess secondary categorical outcomes using discrete Cox proportional hazards models.¹⁸⁴

15f. Subgroup analyses. For the vitamin D intervention, prespecified subgroup analyses will be based on baseline total and bioavailable serum 25(OH)D concentrations, urine ACR, and eGFR as well as race/ethnicity: we hypothesize that effects will be greater among participants who have low 25(OH)D at baseline, who have DKD (urine ACR ≥ 30 mg/g or eGFR < 60 mL/min/m 2) at baseline, or are Caucasian.^{185,186} For the omega-3 fatty acid intervention, prespecified subgroup analyses will be based on baseline levels of EPA+DHA and hsCRP: we hypothesize that effects will be greater among participants who low levels of EPA+DHA or high concentrations of hsCRP at baseline. Effect modification will be tested by including interaction terms of treatment assignment with subgroup in linear mixed models (Equation 2).

15g. Exploratory adherence and efficacy analyses. All primary analyses will be performed according to the intent-to-treat principle (Section D15e). We plan secondary, *exploratory* analyses for the following limited purposes: (a) to evaluate whether null findings, if observed, are robust (i.e. not readily attributable to defects in the study interventions or their administration); and/or (b) to more comprehensively evaluate the potential range of treatment effects, if treatment effects are observed. We understand and acknowledge that these analyses, which are based on data collected after randomization, may introduce bias into study results. We will therefore use caution to limit their interpretation. We will first repeat analyses among the subset of participants who report continuous adherence to $\geq 80\%$ of study medications. In addition, we will assess whether changes in 25(OH)D and EPA+DHA levels are associated with changes in urine ACR and eGFR. For the latter analyses, change in 25(OH)D concentrations or change in EPA+DHA concentration (continuous variables) will replace treatment assignment in linear mixed models.

D16. Power. We calculated power using simulation (2000 replications) and the following assumptions: independent and equal allocation of participants to each treatment; 1,058 participants (80%) contributing at least one follow-up blood sample (as supported in Section D10); variation in eGFR and its change over time as observed in the preliminary data from our study population (Section D12); and no interaction between treatments. With these assumptions, we have 80% power (two-sided alpha=0.05) to detect a 2.3 mL/min/1.73m 2 difference in eGFR at year 5, comparing each active treatment to placebo. Power for alternative effect sizes is shown in Figure 7. We do not present power for secondary outcomes because the incidence of these outcomes is difficult to predict with available data.

[figure not shown]

Figure 7. Study power by effect size for the primary outcome (difference in estimated GFR in mL/min/1.73m 2).

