As an additional secondary outcomes, we will examine the proportion of participants who develop a composite outcome of albuminuria progression (100% increase in urine ACR *and* a year 4 urine ACR ≥ 30 mg/g), rapid loss of eGFR (loss of eGFR ≥ 12 mL/min over the 4-year interval), ESRD (maintenance dialysis or kidney transplant verified by medical records review), and/or death. This composite outcome serves two purposes. First, it addresses large changes in DKD which have particularly high clinical impact. Second, the composite outcome reduces the potential impact of competing risks that preclude assessment of urine ACR and/or eGFR at follow-up. Accounting for competing risks will be particularly important if the incidence of ESRD and/or death differs by treatment assignment. The composite endpoint is scientifically important, because each component is a clinically relevant diabetes outcome and progression of DKD is strongly associated with ESRD and death. A 100% increase in urine ACR is generally considered to have clinical relevance, and additional inclusion of a threshold (30 mg/g) will reduce the potential impact of measurement error among persons with “normal” levels of albuminuria near the limits of assay reliability. Loss of eGFR exceeding 12 mL/min over the 4-year interval (3mL/min/year) has been associated with increased risk of mortality among older adults with and without diabetes.^{34, 37}

VI.d. Interaction of cholecalciferol and ω -3 FA. We will assess for interaction of the study interventions (vitamin D and ω -3 FA) for each of the primary and secondary study outcomes. First, we will assess for interaction on the additive scale. Differences in each study outcome comparing the treatment group which

receives both active study medications (vitamin D + ω -3 FA) to the treatment group which receives neither (placebo + placebo) will be compared to the sum of differences comparing treatment groups receiving only one medication (vitamin D + placebo, or placebo + ω -3 FA) to the treatment group which receives neither (placebo + placebo). Interaction on the additive scale exists if the former difference differs significantly from the sum of the latter two differences.¹⁵¹ Second, we will assess for interaction on the multiplicative scale by testing the joint effect of assigned treatment on each study outcome using ANCOVA. For urine ACR:

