where β_2 represents the difference in eGFR comparing active vitamin D₃ to placebo, and the corresponding 95% confidence interval and p-value reflect statistical significance of the treatment effect. Parallel equations will be used to test effects of ω -3 FA on changes in albuminuria and eGFR in the absence of interaction with vitamin D₃. An alpha level of 0.05 will be taken to represent statistical significance, without correction for multiple comparisons. We will examine the distributions of change in urine ACR and eGFR and substitute rank-sum comparisons if indicated.¹⁵² We will test differences in proportions of participants attaining the composite dichotomous outcome using the χ^2 test.

Analyses will be performed in accordance with the intent-to-treat principle. For analyses of change in urine ACR and eGFR as continuous variables, only participants who complete study measurements at baseline and year 4 will be included in analyses (complete case analysis). Maximum effort will be made to ensure that all possible participants supply follow-up biospecimens, and all available participants will be included in continuous outcome analyses regardless of adherence to study medications. The relatively large sample size makes it likely that few or no substantial differences in baseline characteristics will be present. In the event that any baseline characteristics are not balanced between treatment groups, however, secondary analyses will add to the ANCOVA model additional terms for such baseline characteristics. If we observe differences by treatment group in medication use (e.g. glucose-lowering or antihypertensive medications) or laboratory covariates (e.g. hemoglobin A1c, CRP) over follow-up, we will explore whether such differences may mediate or obscure effects of study interventions on study outcomes by including additional covariate(s) in the ANCOVA model to assess change in β_2 (treatment effect) toward or away from zero, respectively.

VI.f. *Subgroup analyses.* For the vitamin D intervention, prespecified subgroup analyses will be based on baseline plasma 25(OH)D concentration, baseline urine ACR, baseline eGFR, and race/ethnicity. We hypothesize that beneficial effects of cholecalciferol on urine ACR and eGFR will be greater among

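### The addendum's intention-to-treat rule, at least one follow-up biosample, is not limited to eGFR and ACR; applied as written, it leaves deaths without a sample out of the secondary composite.

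*Combined protocol and SAP*

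**What the plan says.** **Analysis set.** Protocol Addendum 15c says analyses follow intention to treat, "meaning that all participants who return at least one follow-up biosample will be included in analyses". It names no outcome. Its only missing-data method is multiple imputation of year 5 eGFR, "utilizing baseline data as well as eGFR and urine ACR data available at year 2".

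**Composite.** 15b defines a secondary time-to-event composite of 40% eGFR loss, ESRD verified from medical records, or death. One stated reason is that it "reduces the potential impact of competing risks that preclude assessment of eGFR at follow-up". The analysis is given in 15e: "We will assess secondary categorical outcomes using discrete Cox proportional hazards models". No analysis set is stated there.

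**Sampling.** 15a refers to participants who "complete year 2 and 5 year biosample collections". D16 plans on "1,058 participants (80%) contributing at least one follow-up blood sample".

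**Original protocol.** VI.e tied its sample restriction to named outcomes: "For analyses of change in urine ACR and eGFR as continuous variables, only participants who complete study measurements at baseline and year 4" were to be included. VI.c said of its own composite: "Accounting for competing risks will be particularly important if the incidence of ESRD and/or death differs by treatment assignment".

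**The concern.** Someone who dies before the year 2 collection cannot return a follow-up sample. If 15c governs the composite, that death is not counted. Nor is a later death or an ESRD case in a person who never returned a sample. Neither component needs a biosample to be observed, and an early death is the clearest example of the competing risk that 15b wants to capture.

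Inclusion would then depend on something that happens after randomisation. Any effect of either agent on early death would be missed. The comparison would be biased if return differs by arm and is related to risk. If neither applies, the comparison stays valid but rests on fewer events. The baseline comparison of returners with non-returners in 15a describes this selection but does not restore the events.

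**Working it through.** **1. Text.** 15c is general and follows 'meaning that', so it reads as the definition of the intention-to-treat set. Nothing in 15b to 15g gives the composite a different set. The outcome restriction in VI.e of the original protocol was not carried over.

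**2. The plan's own composite power (original protocol, VI.h).** The addendum gives none. VI.h states 80% power at relative risks of 0.69 to 0.76 and 90% at 0.65 to 0.73, for 20% to 30% incidence. I used a two-proportion test, two-sided alpha 0.05, no continuity correction, and 1,500 × 0.80 / 2 = 600 per group:

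| Incidence | Relative risk | Stated power | Recomputed |
|---|---|---|---|
| 20% | 0.69 | 80% | 81.8% |
| 30% | 0.76 | 80% | 80.8% |
| 20% | 0.65 | 90% | 90.5% |
| 30% | 0.73 | 90% | 89.4% |

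At 750 per group the first two would be 89.4% and 88.6%. The original composite was therefore powered on the 1,200 expected to return. VI.h uses a different composite definition, so its 20% to 30% incidence does not carry over to the addendum.

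**3. Inputs for the size.**
- Enrolled: N = 1,058 / 0.80 = 1,322.5 (D16), so about 264 have no follow-up sample.
- Four-year mortality m: 4.6% in VI.h, borrowed from an observational cohort. III.a excludes clinically apparent CVD and cancer, so it may be high here. I use 2% (assumed) and 4.6%.
- Hazard shape k: 1 (constant), 1.5 and 2 (rising); assumed.
- 40% eGFR loss: the documents give no incidence. I assume 3% to 10% of 1,058, which is 31.7 to 105.8 events.

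**4. Formulas.** H = −ln(1 − m); F(t) = 1 − exp(−H (t/4)^k). Deaths before year 2 = N·F(2); deaths by year 5 = N·F(5). Composite events = N·F(5) + eGFR-loss events, with no overlap and ESRD ignored. Share lost = N·F(2) / composite events. Standard error factor for the log hazard ratio = 1/√(1 − share).

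Example, m = 4.6%, k = 1: H = 0.0471; F(2) = 2.33%, or 30.8 deaths; F(5) = 5.72%, or 75.6 deaths; 30.8/75.6 = 40.7%. With 3% eGFR loss, 30.8 / (75.6 + 31.7) = 28.7%, and 1/√(1 − 0.287) = 1.18.

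**5. Results.**

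| m | k | Deaths before year 2 / by year 5 | Share of deaths | Share of composite (3% / 10% loss) |
|---|---|---|---|---|
| 2% | 1 | 13.3 / 33.0 | 40.3% | 20.5% / 9.6% |
| 2% | 1.5 | 9.4 / 36.8 | 25.6% | 13.7% / 6.6% |
| 2% | 2 | 6.7 / 41.1 | 16.2% | 9.1% / 4.5% |
| 4.6% | 1 | 30.8 / 75.6 | 40.7% | 28.7% / 17.0% |
| 4.6% | 1.5 | 21.8 / 84.2 | 25.9% | 18.8% / 11.5% |
| 4.6% | 2 | 15.5 / 93.8 | 16.5% | 12.3% / 7.8% |

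The standard error factor runs from 1/√(1 − 0.045) = 1.02 to 1.18. Later deaths among never-returners would add to the loss; the documents give no figure for them.

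**6. Is censoring non-returners at baseline a safe alternative?** Suppose there is no treatment effect, 2.33% die by year 2 in both arms, and 85% v 75% of survivors return (assumed). If survivors without a sample are censored at baseline, the first risk set holds all deaths plus returning survivors only. The death risks become 0.0233 / (0.0233 + 0.9767 × 0.85) = 0.0273 and 0.0233 / (0.0233 + 0.9767 × 0.75) = 0.0308, a spurious ratio of 0.89. Adding a 3% risk of eGFR loss gives 0.94. With 82% v 78% return the ratios are 0.95 and 0.98.

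**The case against.** The sentence in 15c includes; it does not exclude. It says 'all', not 'only', and its closing clause suggests its main aim is to keep non-adherers. The rest of 15c concerns year 5 eGFR, and 15g restates intention to treat for primary analyses. 15b is the specific text on the composite; it counts death and verified ESRD and says why. On that view a sensible analyst would count early deaths, and only a wording change is needed.

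Much of this stands. The scope is ambiguous, and a reader might infer from 15c that the sponsor means to discard early deaths; the documents do not support that. But none of these passages supplies an analysis set for the composite, so two careful analysts could build different composites from the same plan.

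A reader might also infer that the original protocol was free of the problem. That goes too far: it limited its sample restriction to the continuous outcomes, but it named no explicit set for its composite and powered it on the 1,200 expected to return.

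The addendum cites sections D10 and D12, which are not in the file. Follow-up of non-returners may be described there.

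**Conclusion.** The concern holds as a scope gap that conflicts with the stated purpose of the composite. It is worth fixing before analysis, but it affects a secondary outcome for which the addendum makes no power claim.

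Under the assumptions shown, deaths before year 2 are about 16% to 41% of five-year deaths and about 5% to 29% of composite events. Losing them raises the standard error by about 2% to 18%. The upper end needs constant hazard, 4.6% mortality and only 3% eGFR loss together. The run-in and the health exclusions make lower early mortality plausible. A larger loss would need mortality above 4.6%, for which the documents give no support.

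A reader might infer that the primary result is compromised too. This point does not show that: leaving these deaths out of the composite does not change the primary eGFR estimate, although that analysis uses the same set of returners. Nor do the documents show that return will differ by arm. The parent trial is double-blind, and the return splits in step 6 only illustrate what could happen.

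**What to change.** 1. State in 15c that the requirement for at least one follow-up biosample applies only to the eGFR and ACR change analyses.
2. Analyse the composite in all randomised sub-cohort participants as assigned, counting deaths and verified ESRD whether or not a sample was returned.
3. Report death or ESRD alone in the same full set beside it, since that needs no biosample.
4. State in advance how living, ESRD-free people with no follow-up sample enter the composite. Censoring them at baseline can bias the ratio if return differs by arm. Multiple imputation is one option for a sensitivity analysis; it would have to assign the interval of the loss (year 2 or year 5), and it would rest on baseline data and assigned treatment alone, because these people have no year 2 values.

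The cost is a few sentences in the plan and a little more analysis. Vital status for non-returners must be confirmed through parent-trial follow-up.
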